#### 5.1.2. Number of subjects

Three hundred and thirty (330) randomized subjects are planned in total (approximately 55 subjects per group).

#### 5.1.3. Study region/location

Approximately 60 investigational sites in the US and Europe will conduct the study. Potential back-up sites will be identified and qualified and will be activated in case of recruitment issue. Recruitment will be competitive between sites.

### 5.2. ENTRY CRITERIA

#### 5.2.1. Inclusion Criteria

To be eligible for inclusion into this study, the subject must **fulfill all** of the following criteria:

1. The subject must provide written informed consent prior to initiation of any study related procedures.
2. The subject must be a female volunteer aged 18 to 45 years inclusive at screening.
3. The subject must have had surgically and - if available - histologically confirmed pelvic endometriosis (laparoscopy, laparotomy, vaginal fornix or other biopsy) up to 7 years before screening.
4. The subject has moderate to severe endometriosis-associated pain during the screening period defined as:
  - a. At the screening visit, a score of at least 2 for dysmenorrhea AND at least 2 for non-menstrual pelvic pain for the previous month assessed with the mB&B scale.
  - b. Over two full menstrual cycles (i.e. from day 1 of the first menstruation going over two spontaneous menstrual cycles up to the day before the next menstruation i.e. the third menstruation) finishing just before the baseline visit:

- i. Mean overall pelvic pain scores of at least 4 on the 0–10 NRS over the 5 days with the highest score for each cycle separately, i.e. required for both cycles;
  - ii. At least two days with “moderate” or “severe” pain on the 0–3 VRS for pelvic pain over the days with uterine bleeding for each cycle separately, i.e. required for both cycles;
  - iii. At least two days with “moderate” or “severe” pain on the 0–3 VRS for pelvic pain over the days without uterine bleeding for each cycle separately, i.e. required for both cycles.
5. The subject is compliant with e-diary and has completed it on at least 80% of days during the two screening menstrual cycles.
6. The subject has regular menstrual cycles and the total length of the two screening menstrual cycles should be between 42 to 76 days.
7. The subject has a BMI  $\geq 18$  kg/m^2 and  $\leq 39$  kg/m^2 at the screening visit.
8. If of childbearing potential, the subject agrees to use one of the following birth control methods during the entire treatment period of the study:
  - a. Sexual abstinence,
  - b. Partner with a vasectomy with confirmed azoospermia,
  - c. Double non-hormonal barrier contraception such as condom or diaphragm each combined with spermicide.
9. If of non-childbearing potential, the subject must have had tubal ligation sterilization at least two months before the screening visit.
10. The subject must be able to communicate well with the Investigator and research staff and to comply with the requirements of the study protocol.

### 5.2.2. Exclusion Criteria

To be eligible for inclusion in this study the subject must **not** meet any of the following criteria:

1. The subject is pregnant or breast feeding or is planning a pregnancy within the duration of the treatment period of the study.
2. The subject is less than 6 months postpartum or 3 months post-abortion/miscarriage at the time of entry into the screening period.
3. The subject had an interventional surgery for endometriosis performed within a period of 60 days before screening.
4. The subject had a hysterectomy or bilateral ovariectomy.
5. The subject had a tubal sterilization which was performed with ESSURE™.
6. The subject has an in situ copper intra-uterine device (IUD) or an IUD with progestogen.

7. The subject had endometrial ablation resulting in amenorrhea.
8. The subject has at least one ovarian endometrioma with a diameter of 7 cm or greater.
9. The subject is likely to require treatment during the study OR received treatment within a specified period prior to screening with any of the medications listed below:
  - a. Gonadotropin releasing hormone (GnRH) antagonists 3 months
  - b. GnRH agonist injections/ 3-month depot injections 3 months/6 months
  - c. Danazol 3 months
  - d. Oral contraceptives and other sex hormones 1 month
  - e. Depot contraceptives 6 months
  - f. Selective Progesterone Receptor Modulators (SPRMs),  
Selective Estrogen Receptor Modulators (SERMs)  
and aromatase inhibitors 3 months
  - g. Long acting analgesics (i.e. requiring less than  
once daily dosing) 1 day
  - h. Systemic glucocorticoid treatments  
for acute diseases (not depot) 1 month
10. The subject has a history of or current systemic glucocorticoid therapy for treatment of chronic diseases (e.g. Systemic Lupus Erythematosus (SLE), rheumatic arthritis).
11. The subject did not respond to prior treatment with GnRH agonists or GnRH antagonists for endometriosis.
12. The subject has alanine aminotransferase (ALT), aspartate aminotransferase (AST), or total bilirubin levels  $\geq 2$  times the upper limit of normal OR gamma-glutamyl transpeptidase (GGT) level  $\geq 3$  times the upper limit of normal at screening.
13. The subject has a known positive HIV or viral Hepatitis serology.
14. The subject has abnormal uterine bleeding of undiagnosed cause.
15. The subject had/had clinically significant findings from a PAP (Papanikolaou) smear performed within the past 12 months or at the screening visit which will require surgical intervention (e.g. Loop electrosurgical excision procedure (LEEP) or cervical conisation).
16. The subject has chronic pelvic pain that, in the opinion of the Investigator, is not caused by endometriosis and requires chronic analgesic or other chronic therapy, or that would interfere with the assessment of endometriosis related pain.
17. The subject has any other clinically significant gynecological condition identified on screening transvaginal ultrasound (TVUS) or endometrial biopsy, which might interfere with the study efficacy and safety objectives. However, uterine fibroids (as long as uterus size  $\leq 12$  weeks, i.e. equivalent gestational weeks) and adenomyosis are allowed.
18. The subject has a history of, or known osteoporosis or other metabolic bone disease.

19. The subject has any known condition, including findings in the medical history or in the screening assessments, which in the opinion of the Investigator constitutes a risk or a contraindication to the participation of the subject in the trial or that could interfere with the trial objectives, conduct or evaluation.
20. The subject has a mental condition rendering her unable to understand the nature, scope and possible consequences of the study, or evidence of an uncooperative attitude.
21. The subject has current problem with alcohol or drug abuse (including painkiller abuse).
22. The subject has been administered with any experimental drug in the 12 weeks before dosing.

## 6. STUDY PROCEDURES AND ASSESSMENTS

### 6.1. GENERAL INSTRUCTIONS

Before the start of the study, each subject will be provided with a subject information leaflet giving details on the Investigational Medicinal Product (IMP), study procedures and potential risks and they will also be informed verbally by the Investigator or medical delegate of the overall requirements of the study. They will be instructed that they can obtain further information from the Investigator at any time and that they are free to withdraw their consent and to discontinue their participation in the project at any time without prejudice.

If the subject is willing to participate in the study, she will be requested to give written informed consent prior to conducting any of the study screening procedures after being given sufficient time to consider her participation and the opportunity to ask for further details. Two original copies of the consent form will be signed and personally dated by both the subject and the Investigator or medical delegate. One original signed copy will be kept by the Investigator in the confidential investigator file and the second original signed copy will be given to the subject. Although nursing staff may be involved in describing the trial to a subject, the Investigator/medical delegate must participate in discussions with the subject and personally sign and date the informed consent form (ICF).

The subject will be asked if she authorizes the Investigator to notify her general practitioner of her participation in the trial.

Upon signature of the ICF, each subject will be assigned a Subject Identification Number (SIN) in the electronic Case Report Form (eCRF). Subject Identification Numbers will be made of 5 digits, as follows:

- 1st digit: country identifier (1 to 4)
- 2nd and 3rd digits: site identifier (01 to 99)
- 4th and 5th digits: subject number (01 to 99)

During the whole study, the subject will be identified using the SIN for all documentation and discussion. The SIN assigned to a subject in this way must only be used for that subject.

Should a subject drop out from the study, the SIN will not be re-allocated.

An eCRF will be completed for all subjects who signed the ICF. When a subject is subsequently not enrolled in the study, the reason for non enrollment will be recorded in the eCRF.

When a subject has been found to be eligible for the study, the subject will be randomized to one of the 6 treatment groups in a 1:1:1:1:1:1 ratio (approximately 55 subjects per treatment arm) as shown in Figure 1.

Randomization will be done according to a computer-generated list. Treatment assignments will be obtained via the IWRS according to the randomization list. The subject will be allocated a randomization number and a treatment kit number via the IWRS. The randomization number allocated to the subject will allow any unblinded study personal to identify the treatment group to which the subject is randomized. The treatment kit number will correspond to the kit number indicated on the label of the study drug. Kit numbers will start from K0001, K0002, K0003 etc. (5-characters).

At the end of Part A, to maintain the blind and prevent identification of the titrated subjects, all subjects will be allocated a new treatment kit number via IWRS for the 12-week Part B treatment period.

Treatment will remain blinded up to the end of the study for the Investigator and the subject.

## **6.2. OUTLINE OF STUDY PROCEDURES AND ASSESSMENTS**

All post-baseline visits should take place at the end of the defined period (i.e. week 4 visit should be scheduled at the end of week 4, week 8 visit should be scheduled at the end of week 8, etc.). Post-baseline visits dates are calculated from Day 1 visit date.

### **6.2.1. Screening Period – Study Screening visit (11±5 weeks prior to Day 1 visit)**

The subject will be informed of the study objectives and overall requirements, and written informed consent will be obtained before performing any study-specific procedures that are not standard of care.

The subject will be considered as included into the study after the ICF is signed and dated by the subject and the Investigator or medical delegate.

The screening period will last up to 11±5 weeks during which the subject will be seen up to three times. During this time the following study screening assessments will be completed (see schedule of assessments in APPENDIX A):

- Demographic data, height and weight
- Medical history including concomitant diseases, obstetric/gynecological history and history of endometriosis including diagnosis and previous treatments
- Assessment of endometriosis pain with the mB&B scale (see APPENDIX B)
- Previous and current treatments recording
- Physical examination
- Vital signs (blood pressure and heart rate)
- Urine pregnancy test

- TVUS of uterus and ovaries to measure endometrium thickness, to rule out any clinically significant gynecological conditions which might interfere with the study efficacy and safety objectives and to confirm that the subject has no ovarian endometrioma  $\geq 7$  cm in diameter
- Gynecological examination, including the mB&B scale (see APPENDIX B) clinical signs reporting (pelvic tenderness and pelvic induration)
- Endometrium biopsy (should be performed at least 7 days after the first day of menstruation and sent for central assessment). If no tissue is available, the biopsy should be repeated as soon as possible in the following days.

The endometrium biopsy is not required at the screening visit for subjects having performed an endometrium biopsy within the past 6 months of the screening visit, which shows no endometrium atypical hyperplasia or adenocarcinoma and for which slides are available for current study assessment through retrospective central laboratory reading.

- PAP smear

A screening PAP smear is not required for subjects in whom a PAP smear was performed within the 12 months prior to the screening visit and which results indicate no clinically significant abnormalities requiring surgical intervention (e.g. LEEP or cervical conisation) and are available for source document verification.

- Manual breast examination (by palpation)
- Blood samples for haematology, coagulation parameters, chemistry, lipids and hormone assessments
- Urinary protein dipstick.
- Contraception counselling

The subject will receive double barrier contraception (condoms with spermicide) if necessary.

In addition, a limited quantity (as per Investigator's judgement) of ibuprofen and/or acetaminophen/paracetamol as standard rescue medication for endometriosis related pain will be given to the subject at the screening visit to cover the screening period.

The subject will be given an eDiary with a user manual to take home and will be trained by the Investigator or delegate on how to correctly use and complete it: she will be asked to record her IMP intake, pelvic pain, dyspareunia, dyschezia, difficulty in performing daily activities, uterine bleeding, impression of severity and use of analgesic drug(s) including dose. These screening assessments should cover at least two full menstrual cycles (from day 1 of the first menstruation going over two spontaneous menstrual cycles up to the day before the next menstruation i.e. the third menstruation). Subject diary completion should be started on the day of screening visit.

The eDiary should be completed:

- Daily, in the evening at approximately the same time, for IMP intake, pelvic pain, dyspareunia, difficulty in performing daily activities, uterine bleeding and use of analgesic drug(s) including dose;
- Weekly, for dyschezia pain;

- 4-weekly, for patient's impression of severity.

Any concomitant medications taken after signature of informed consent will be recorded in the eCRF (excluding provided analgesics taken for endometriosis related pain which will be recorded daily in the eDiary).

Any AE occurring after signature of informed consent will be recorded in the eCRF.

The subject will be asked to return to the site between the first and seventh day (inclusive) of her next menstrual period (the period after the 2 screening menstrual cycles) for the Day 1 visit. Final assessment of her eligibility will be performed including the minimum baseline scores for pelvic pain collected via the eDiary. The baseline mean pelvic pain scores will be calculated during the screening period over two full, spontaneous menstrual cycles.

If for logistical reasons beyond her control, the subject is unable to come to the clinic for Day 1 within the acceptable time window (1st to 7th day inclusive of the cycle) then the subject will be allowed to start Day 1 in the following cycle (again on the 1st to 7th day of the cycle). In this case, the eligibility assessments should be assessed based on the first two cycles only. However, the eDiary recording should be continued daily during the third cycle.

#### **6.2.2. Part A treatment period**

During the whole study Part A, the subject will be asked to record on her eDiary:

- Daily, at approximately the same time each evening, her IMP intake, pelvic pain, dyspareunia, difficulty in performing daily activities, uterine bleeding and use of analgesic drug(s) including dose;
- Weekly, her dyschezia pain;
- 4-weekly, the patient's impression of severity.

##### **6.2.2.1. Baseline visit – Study visit Day 1**

If the subject has successfully completed all screening assessments and is between the first and seventh day (inclusive) of starting menstruation, she will go to the investigational site for the following evaluations and tests before drug administration:

- Confirm inclusion/exclusion criteria (randomization will not be postponed if the results of the endometrium biopsy done during the screening period are not available on Day 1)
- Previous and concomitant treatments recording
- AE recording
- Physical examination
- Vital signs (blood pressure and heart rate)
- Urinary protein dipstick
- eDiary check for good completion

- EHP-30 questionnaire (see APPENDIX C) completion by the subject
- Urine pregnancy test
- Contraception counselling

The subject will receive double barrier contraception (condoms with spermicide) if necessary. It will be provided upon need at each subsequent visit over the duration of the study.

In view of the invasive nature of the following assessments it is recommended to perform these upon confirmation from the eDiary data that the subject meets the study entry requirement and upon receipt of the screening central laboratory results and confirmation that the values meet the study entry requirement. The following procedures will be performed and recorded as part of the screening/baseline assessments, prior to the first administration of study treatment:

- Fasting blood samples for haematology, coagulation parameters, chemistry, lipids, hormones and OBE2109 and KP017 pre-dose plasma levels assessments.
- BMD assessed by DXA for femoral neck, hip and spine. DXA can be performed up to 10 days after baseline.

The DXA scans will be read centrally.

The subject will then be randomized to one of the six treatment groups and will be provided with the study drug and analgesics. The subject will be instructed on how to take the study medication, analgesics, and on how to record the administration in the eDiary. The analgesics provided will be used only as rescue medication; no prophylactic use of analgesics is allowed during the whole study. The subject will be provided as necessary with analgesics at each subsequent visit to cover study period until Week 36.

From Day 1 up to the next scheduled study visit, the subject will be asked to record in the eDiary her IMP intake, pelvic pain, dyspareunia, difficulty in performing daily activities, uterine bleeding, dyschezia, impression of severity and use of analgesic drug(s) including dose.

The subject will take her first dose of study medication at the study site.

After **OBE2109/placebo administration**, the following procedure will be performed:

- Post-dose PK samples taken about 1.5 to 2.0 h after drug administration.

Upon completion of the visit, the subject will be provided with emergency contact numbers and will be scheduled for her next visits.

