### 3.2. SAFETY ENDPOINTS

- Change from baseline to weeks 12, 24 and 48 in BMD assessed by dual-energy X-ray absorptiometry (DXA) for femoral neck, hip and spine.
- Treatment emergent adverse events (TEAEs) frequency and severity.

- Changes in clinical laboratory assessments (haematology, coagulation parameters, biochemistry, hormones, lipids and urinalysis) from baseline to weeks 4, 8, 12, 16, 20, 24, 28 and 36.
- Any pathological changes from baseline in the endometrium as assessed by histology from endometrial biopsies performed at weeks 12 and 24 (and week 36 only if no endometrial biopsy was obtained at week 24 or diagnosis at week 24 was different from “benign endometrium”).

Change from baseline in any other safety parameter including weight, vital signs, gynecological assessment, breast assessment and endometrial thickness.

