#### **6.2.2.3. Study visit Week 12 (Day 85 ± 3 days) – End-of-Part A visit**

The subject will take her last daily dose of Part A study medication at the usual time in the morning at home. The approximate time of dose administration and time of taking of the blood sample will be recorded in the eCRF.

The following tests and evaluations will be performed at week 12 Study Visit:

- Assessment of endometriosis pain with the mB&B scale (see APPENDIX B)
- Previous and concomitant treatments recording
- AE recording
- Physical examination
- Vital signs (blood pressure and heart rate)
- Gynecological examination, including the mB&B scale (see APPENDIX B) clinical signs reporting (pelvic tenderness and pelvic induration)
- TVUS of uterus for measuring endometrium thickness and of ovaries for checking their normality.
- Urine pregnancy test
- Contraception counselling
- eDiary check for good completion

- EHP-30 (see APPENDIX C) and PGIC (see APPENDIX D) questionnaires completion by the subject
- Post-dose PK samples (the approximate time of dose administration at home and time of taking of the PK sample will be recorded)
- Blood samples for haematology, coagulation parameters, chemistry, lipids, hormones
- Urinary protein dipstick
- Endometrium biopsy, unless the endometrium thickness in TVUS is  $\leq 5$  mm, in which case no endometrium biopsy will be necessary, as far as the screening biopsy has provided assessable results. Appropriate photo documentation of the endometrium thickness is mandatory and will be kept in the source documents.
- BMD assessed by DXA for femoral neck, hip and spine. DXA can be performed  $\pm 10$  days from study visit.

The subject will be allocated a new treatment kit number via IWRS for the 12-week Part B treatment period. The subject will take her first daily dose of Part B study medication at home in the morning of the day following the Week 12 study visit.

Week 12 study visit constitutes the end of Part A visit.

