**Part B – 3-monthly treatment: 13 pouches/3-monthly kit – 26 blisters (13 blisters of each color) – 7 tablets/blister.**

Population	55	55	55	55	55	55
Arm	Placebo/100mg	50mg	75mg	100mg	200mg	50 or 75 or 100mg
Blister with color A						
Blister with color B						

On Day 1 and at Week 12 visit, the subject will be given one 3-monthly kit for a total of 13 weeks (i.e. including one extra week to cover the allowed time window for visit scheduling).

Each day, from Day 1 to the last day of Week 24 inclusive, the subject will have to swallow two tablets, one from each blister of different color and included in a same pouch.

In each 3-monthly kit, all 13 pouches will have a label including a tear-off part. The non-tear off part will remain affixed to the pouch and one of the 13 tear-off part containing the study number and the kit number will be placed into a drug accountability booklet at site.

Labels will be printed in the local language of the countries where the study will take place in accordance with applicable local regulations, the recommendations of GMP guideline (Annex 13) and FDA 21 CFR 312.6 part.

The label on the secondary packaging will indicate at least the following items:

- Protocol number
- Kit number
- Batch number
- Storage conditions
- Sponsor name and address
- Expiry date (for EU only)

Label examples are filed in the study file at the Investigator's site and in the trial master file.

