### **9.5.1. Baseline Assessment**

Descriptive statistics will be performed on relevant screening and baseline data (i.e. data collected prior to the treatment administration) and on demographic characteristics for each treatment group and overall. There will be no formal comparison of baseline data, that is, no statistical hypothesis testing.

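### The baseline DXA is listed as a pre-dose procedure but may be done up to 10 days after Day 1, so in subjects scanned late any early bone loss is counted in the baseline

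*Combined protocol and SAP*

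**What the plan says.** Section 6.2.2.1 (baseline visit, Day 1) introduces a short list with "The following procedures will be performed and recorded as part of the screening/baseline assessments, prior to the first administration of study treatment". The list contains the fasting blood samples and the DXA of femoral neck, hip and spine. The DXA item adds: "DXA can be performed up to 10 days after baseline".

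The same section fixes the first dose at that visit: "The subject will take her first dose of study medication at the study site". Section 7.3 makes dosing daily from then on: "Each day, from Day 1 to the last day of Week 24 inclusive, the subject will have to swallow two tablets".

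Section 9.5.1 describes the baseline summaries as covering "relevant screening and baseline data (i.e. data collected prior to the treatment administration"). The first safety endpoint in Section 3.2 is "Change from baseline to weeks 12, 24 and 48 in BMD assessed by dual-energy X-ray absorptiometry (DXA) for femoral neck, hip and spine".

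Section 6.4.4 says only that BMD is assessed at baseline and weeks 12, 24 and 48. Appendix A marks the scan at Day 1 without a footnote. Neither says whether a scan taken after the first dose counts as baseline. Section 9.5 leaves analysis detail to a SAP still to be written, and the combined document carries no separate SAP text.

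**The concern.** The introduction to the list and the DXA item cannot both hold. A site that follows the item may take the baseline scan after up to 10 days of study drug.

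Every BMD change is measured from that scan. If the drug causes bone loss from the start of dosing, whatever is lost before a late scan disappears from the measured change. The error runs one way in the active arms, towards less loss. Placebo subjects in Part A have no drug-related loss to hide, so the active-placebo difference at week 12 is pulled towards zero. For a safety endpoint that is the unfavourable direction. BMD is also one of the variables in the exposure-response objective (Section 2.3).

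Late scans are plausible. Section 6.2.2.1 recommends holding these procedures until eDiary and central laboratory eligibility are confirmed, Day 1 must fall on days 1 to 7 of menstruation, and the stated DXA window runs only forwards from baseline.

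**Working it through.** **No plan figure to reproduce.** The plan states no sample size, power or precision for BMD. Its one sample-size figure (55 per arm, Section 9.2) rests on pain response rates and uses no BMD input.

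**Timing, statement by statement**

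- Introduction to the list, Section 6.2.2.1: scan before the first dose.
- DXA item, Section 6.2.2.1: scan as late as Day 1 + 10 = Day 11.
- First dose: Day 1, on site (Section 6.2.2.1).
- Dosing: daily from Day 1 (Section 7.3).
- Baseline data: collected before treatment (Section 9.5.1).

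A scan k days after Day 1, with k from 1 to 10, satisfies the second statement and fails the first and the last. It follows k days of treatment.

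**Inputs for the size**

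- Week 12 is Day 85 (Section 6.2.2.3): 85 − 1 = 84 days on treatment.
- Week 24 is Day 169 (Section 6.2.3.2): 169 − 1 = 168 days.
- Largest delay: k = 10 days.
- Assumption: loss is linear in time from the first dose. The documents give no loss rate or time course.

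**Share of the change hidden in one subject** = k / (days from first dose to the later scan)

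| Baseline scan | Week 12 | Week 24 |
|---|---|---|
| Day 1, before dose | 0/84 = 0% | 0/168 = 0% |
| 5 days after Day 1 | 5/84 = 6.0% | 5/168 = 3.0% |
| 10 days after Day 1 | 10/84 = 11.9% | 10/168 = 6.0% |

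With k = 10 the nominal intervals shorten to 84 − 10 = 74 days and 168 − 10 = 158 days. I give no share for week 48, because subjects in follow-up are off treatment after week 24 and linear loss would not be a sensible assumption.

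**In BMD units**, for a range of assumed true week-12 losses L and k = 10: hidden = L × 10/84, measured = L × 74/84.

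| Assumed L | Measured | Hidden (percentage points) |
|---|---|---|
| 0.5% | 0.44% | 0.06 |
| 1% | 0.88% | 0.12 |
| 2% | 1.76% | 0.24 |
| 3% | 2.64% | 0.36 |

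**Averaged over an arm.** If a fraction f of subjects is scanned late with mean delay m days, the mean week-12 change is understated by f × m/84. Neither f nor m is in the documents. As an illustration, take late scans spread evenly over days 1 to 10, so m = 5.5:

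- f = 0.5: 0.5 × 5.5/84 = 3.3%
- f = 1: 5.5/84 = 6.5%

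The arm average reaches 11.9% only if every subject is scanned on the last permitted day.

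**The case against.** The strongest reply is that the 10-day allowance is a deliberate exception under a loosely worded introduction. Eligibility depends on two full cycles ending just before Day 1, Day 1 must fall within a seven-day stretch of menstruation, and there are about 60 sites. A strict pre-dose scan could mean scanning women who then fail screening, or deferring Day 1 by a cycle. The same window applies in every arm and randomization is stratified by site, so late scans should be roughly balanced. Under linear loss the active arms then shrink by similar fractions, and the ordering of doses is not expected to change. Most of this stands. It explains the allowance and limits the harm, but it does not remove the contradiction, and the contrast with placebo is still attenuated.

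A reader might infer more than the documents support:

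- **That scan timing is off by 61 to 97 days against 84.** The extremes are 84 − 10 − 10 − 3 = 61 and 84 + 10 + 3 = 97. They mix the late baseline with the ± 10-day scan window and ± 3-day visit window at week 12, which are symmetric. The 97-day end has its baseline on Day 1 and so no late-baseline error. A placebo subject scanned after the week-12 visit may already have started 100 mg, but that belongs to the week-12 window and not to this point.
- **That BMD will be analysed by nominal week, or through a stated model.** Section 3.2 names the weeks but gives no windowing rule. No BMD model is specified, and Section 9.5.4 makes safety analysis descriptive.
- **That BMD is a main basis for dose choice.** Section 1.6 mentions BMD as background to the E2 range. BMD is one of five safety endpoints.
- **That scan dates are already captured.** This is likely, but it is not stated.

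**Conclusion.** The contradiction is real and sits within one list in Section 6.2.2.1. As written, the plan permits an on-treatment baseline for a named safety endpoint and does not say how to handle one. Where loss occurs on treatment, the effect is to understate it in the active arms and to narrow the Part A difference from placebo.

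The size is modest. Under linear loss from the first dose, 11.9% at week 12 and 6.0% at week 24 are ceilings for a subject scanned 10 days after Day 1. A subject scanned before dosing contributes no error. The average depends on how many scans are late and by how much, which the documents do not say. Loss that is not linear would change the figures in either direction.

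No formal test of safety data is planned, so nothing here touches alpha, power or sample size. This is a minor point worth correcting because the correction is cheap, and not a reason to doubt the BMD endpoint as a whole.

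**What to change.** - **Protocol, Section 6.2.2.1:** reconcile the introduction to the list and the DXA item into one rule for when the baseline scan may be taken relative to the first dose, and make Section 6.4.4 and Appendix A agree with it.
- **Data collection:** make sure the date of every DXA is recorded.
- **SAP:** flag each baseline scan taken after the first dose. Repeat the descriptive summary of BMD change at weeks 12, 24 and 48 without those subjects. Report actual days from first dose to each scan, by arm.

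Section 9.5 schedules the SAP after the protocol is final and before the Part A interim analysis, so these summaries can be pre-specified. The cost is a short wording change and a little more analysis work. A scheduling burden arises only if the reconciled rule requires scans before dosing.
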